2.1.3.1 Primary efficacy endpoint(s)

The primary efficacy variable is the change in HbA1c from baseline to Week 26 which is defined as: HbA1c value at Week 26 - HbA1c value at baseline (%). The primary efficacy variable will be derived in the intent-to-treat (ITT) population, using all HbA1c values regardless of adherence to treatment (ITT estimand). Results for the primary efficacy variable will also be presented in mmol/mol.

2.1.3.2 Secondary efficacy endpoint(s)

All secondary efficacy endpoints are calculated on the randomized periods using the ITT population.

• Change in HbA1c (%) from baseline to Week 52.

At Week 26 and Week 52:

- The percentage of patients with HbA1c <7% (HbA1c responders; Yes/No variable),
- Change from baseline in FPG (in mmol/L and mg/dL),
- Change from baseline in the mean 24-hour plasma glucose concentration, based on the 7-point SMPG profiles (in mmol/L and mg/dL),
- Change from baseline in postprandial plasma glucose excursions (difference between 2-hour postprandial and pre-prandial plasma glucose values at breakfast, lunch and dinner), based on the 7-point SMPG profiles (in mmol/L and mg/dL),
- Change from baseline in 7-point SMPG profiles per time-point (in mmol/L and mg/dL) (fasting pre-breakfast, 2 hours post-breakfast, pre-lunch, 2 hours post-lunch, pre-dinner, 2 hours post-dinner, bedtime).

The process of computation of SMPG variables is described in Section 2.5.

2.1.4 Safety endpoints

The following safety parameters will be analyzed for the main 6-month and 12-month on-treatment periods:

- Hypoglycemia (according to ADA Workgroup on Hypoglycemia) (3),
- Adverse events (AEs), serious adverse events (SAEs),
- Laboratory data,
- Injection site reactions, hypersensitivity reactions,
- Vital signs: heart rate, systolic blood pressure (SBP) and diastolic blood pressure (DBP),
- Body weight.

In case of premature permanent IMP discontinuation, the process described in Section 2.5.3 will be applied to retrieve safety assessments performed at the end of treatment visit (Visit 8000).

Safety observation period

The observation period of safety data will be divided into 3 main segments:

- The pre-treatment period is defined as the time from informed consent up to the time of the first injection of IMP.
- The 12-month on-treatment period is defined as the time from the first injection of IMP up to 1 day after the last injection of IMP.
 - The main 6-month on-treatment period is defined as the time from first injection of IMP up to Week 26 (Visit 9) or up to 1 day after the last injection of IMP, whichever comes earlier.
- The post-treatment period is defined as the time starting 1 day after last injection of IMP (after the on-treatment period).

The on-study observation period is defined as the time from first injection of IMP until the end of the study (defined as the date of end of participation).

2.1.4.1 Hypoglycemia

All hypoglycemia will be reported by patient in e-diary, transferred to the dedicated hypoglycemia event page in the e-CRF and reviewed by the investigator in specific items, or directly completed in another dedicated hypoglycemia event page in the e-CRF by the investigator. For the analyses, the investigator items will be used when available.

All hypoglycemia will be categorized according to the ADA definitions (3) as described below:

- Severe hypoglycemia: Severe hypoglycemia will be derived as an event requiring assistance of another person to actively administer carbohydrate, glucagon, or other resuscitative actions.
- **Documented symptomatic hypoglycemia:** Documented symptomatic hypoglycemia will be derived as an event with symptoms of hypoglycemia and with a measured plasma glucose concentration less than or equal to 3.9 mmol/L (70 mg/dL).
- Asymptomatic hypoglycemia: Asymptomatic hypoglycemia will be derived as an event without symptoms of hypoglycemia but with a measured plasma glucose concentration less than or equal to 3.9 mmol/L (70 mg/dL).
- **Probable symptomatic hypoglycemia:** Probable symptomatic hypoglycemia will be derived as an event with symptoms of hypoglycemia and missing plasma glucose concentration.
- **Relative hypoglycemia:** Relative hypoglycemia (recently termed "pseudohypoglycemia") will be derived as an event with symptoms of hypoglycemia but with a measured plasma glucose concentration greater than 3.9 mmol/L (70 mg/dL).

Any technical details to categorize hypoglycemia in case of missing hypoglycemia information are described in Section 2.5.3.

Hypoglycemia will be evaluated regardless the time of onset during the day.

In addition to the threshold of plasma glucose of less than or equal to 3.9 mmol/L (70 mg/dL), documented symptomatic hypoglycemia and asymptomatic hypoglycemia with a measured plasma glucose concentration less than 3.0 mmol/L (54 mg/dL) will also be analyzed.

Hypoglycemia observation period

- Pre-treatment hypoglycemia are events that occurred during the pre-treatment period.
- Treatment-emergent hypoglycemia are events that occurred during the on-treatment period (see Section 2.1.4).
- Post-treatment hypoglycemia are events that occurred during the post-treatment period.

2.1.4.2 Adverse events variables

All AEs and SAEs will be coded to a LLT, PT, HLT, HLGT and associated primary SOC using the version of MedDRA currently in effect at the sponsor at the time of database lock.

Adverse event observation period

The occurrence of AEs and SAEs is recorded from the time of signed informed consent until the end of the study.

- Pretreatment AEs are AEs that developed or worsened or became serious from the signed informed consent date up to first administration of IMP.
- Treatment-emergent adverse events (TEAEs) are AEs that developed or worsened or became serious during the on-treatment period.
- Posttreatment AEs are AEs that developed or worsened or became serious during the posttreatment period.

Injection site reactions and hypersensitivity reactions

If the investigator or the patient recognizes any sign related to local non-allergic reaction at the injection site, the event should be recorded in the routine AE page in the e-CRF.

Potential hypersensitivity reactions (allergic reactions or allergic-like reactions) will be entered on the AE form and the allergic reaction complementary form should be completed. An Allergic Reaction Assessment Committee (ARAC) will review all possible allergic reactions, independently from the sponsor and in a blinded way regarding the study treatment. The ARAC will review the reported cases, confirm whether or not the event is allergic in nature, and provide a diagnosis for confirmed allergic events, based on the information reported by the investigator.

For the statistical analysis, injection site and hypersensitivity reactions will be identified based on the AE forms (also based on ARAC diagnosis in order not to miss any event), using the following MedDRA codes:

- Injection site reactions will be identified using the following MedDRA searches: under HLGT "Administration site reactions" and HLTs "Administration site reactions NEC", "Injection site reactions", "Infusion site reactions" and "Application and instillation site reactions" and excluding HLTs "Implant and catheter site reactions" and "Vaccination site reactions".
- Hypersensitivity reactions will be identified using the following MedDRA searches: Angioedema standardized MedDRA query (SMQ) [Narrow], Severe cutaneous adverse reactions SMQ [Broad], Hypersensitivity SMQ [Broad and Narrow] and excluding PTs related to administration, application, injection and infusion sites. HLT "Anaphylactic Responses" are included in those SMQs.

Adverse events of special interest

Adverse events of special interest include:

- Alanine aminotransferases (ALT) increase (identified based on the ALT Increase Associated Signs and Symptoms forms),
- Pregnancy of a female subject entered in a study as well as pregnancy occurring in a female partner of a male subject entered in a study with IMP/non-investigational medicinal product (NIMP),
- Symptomatic overdose with IMP/NIMP (identified based on the Overdose forms).

2.1.4.3 Deaths

The deaths observation period are per the observation periods defined above.

- Death on-study: deaths occurring during the on-study observation period,
- Death on-treatment: deaths occurring during the on-treatment period,
- Death post-study: deaths occurring after the end of the study.

2.1.4.4 Laboratory safety variables

Clinical laboratory data consists of blood analysis, including hematology and clinical chemistry. Clinical laboratory values after conversion will be analyzed into international units and international units will be used in all listings and tables. Results will also be presented in conventional US units. The following parameters will be analyzed, grouped by biological function (see study flowchart in Appendix A):

• Hematology:

- Red blood cells and platelets including hemoglobin, hematocrit, red blood cells count and platelets,
- White blood cells including white blood cell count and differential count (neutrophils, lymphocytes, monocytes, basophils, eosinophils).
- Clinical chemistry:
 - Serum lipids including total cholesterol, high-density lipoprotein (HDL) cholesterol, low-density lipoprotein (LDL) cholesterol, and triglycerides (in fasting condition),
 - Electrolytes including sodium, potassium,
 - Renal function including creatinine and estimated GFR (MDRD),
 - Liver function including ALT, aspartate aminotransferases (AST), alkaline phosphatase (ALP) and total bilirubin (in case of values above the normal range, differentiation in conjugated and non-conjugated bilirubin).

Technical formulas are described in Section 2.5.1.

2.1.4.5 Vital signs variables

Vital signs include heart rate (bpm), and systolic and diastolic blood pressure (mmHg) in sitting position (see study flowchart in Appendix A).

Body weight (kg) will be presented with vital signs.

2.1.4.6 Electrocardiogram variables

Not applicable.

2.1.4.7 Immunogenicity variables

If a patient discontinues the treatment prematurely, the process described in Section 2.5.3 will be applied to retrieve immunogenicity assessments performed at the end of treatment visit (Visit 8000).

AIA assessments will be determined in a blinded fashion at a central laboratory (see study flowchart in Appendix A) using a validated anti-insulin antibody binding assay methodology. Only samples collected at least 8 hours after the last administration of mealtime insulin will be taken into account in the analysis.

Anti-insulin antibodies evaluation will consist of:

- Anti-SAR341402/ NovoLog/NovoRapid antibody positive/negative status
- Anti-SAR341402/ NovoLog/NovoRapid antibody titer
- Cross-reactivity to human insulin positive/negative status

The following definitions will be used to identify patients with a change in AIA response during the on-treatment period (see Section 2.1.4 [4]):

- Patients with treatment-induced AIAs will be defined as patients with AIAs that developed de novo (seroconversion) following the IMP administration (ie, patients with at least one positive AIA sample at any time during the on-treatment period, in those patients without pre-existing AIA or with missing sample at baseline).
- Patients with treatment-boosted AIAs will be defined as patients AIA positive at baseline that were boosted to a significant higher titer following the IMP administration (ie, patients with at least one AIA sample with at least a 4-fold increase in titers compared to baseline value at any time during the on-treatment period, in those patients with preexisting AIA). The 4-fold increase in titer corresponds to an increase of two dilution steps within the titration experiment. A single dilution difference (2-fold titer increase) is within the expected imprecision of the titration method and is therefore not considered a relevant change.

Patients with treatment-emergent AIA (Yes, No, Inconclusive) will be derived as follows:

- Patients with treatment-emergent AIAs (AIA incidence) will be defined as patients with treatment-induced or treatment-boosted AIAs.
- Patients without treatment-emergent AIAs will be defined as patients without treatment induced or treatment-boosted AIAs.
- Inconclusive patients will be defined as patients who cannot irrefutably be classified as patients without treatment-emergent AIAs. Inconclusive patients will not be included in the above categories and will be listed separately.

Treatment-emergent AIAs at last on-treatment value (Yes, No, Inconclusive) will be defined using the same definitions based on results obtained at the last on-treatment visit (ie, taking into account the closest value prior to the last dose of IMP).

The peak titer will be defined as the maximal titer observed during the on-treatment period. For patients with treatment-induced and treatment-boosted AIAs, the kinetics of AIA response will be further classified as follows:

• Transient AIA response, defined as a response detected only at one sampling time point during the on-treatment period (excluding the last sampling time point); or response detected at two or more sampling time points during the on-treatment period, where the first and last AIA-positive samples (irrespective of any negative samples in between) are separated by a period less than 16 weeks, and the patient's last sampling time point is AIA-negative.

- Persistent AIA response, defined as a response detected at two or more sampling time points during the on-treatment period, where the first and last AIA-positive on-treatment sample (irrespective of any negative samples in between) are separated by at least 16 weeks.
- Indeterminate AIA response, defined as a response where only the last sampling time point is positive or the last 2 sampling time points are positive but separated by a period less than 16 weeks.

2.1.5 Pharmacokinetic variables

Not applicable.

2.1.6 Pharmacodynamic/genomics endpoints

Not applicable.

2.1.7 Quality-of-life endpoints

Not applicable.

2.1.8 Health economic endpoints

Not applicable.

2.2 DISPOSITION OF PATIENTS

This section describes patient disposition for both patient study status and the patient analysis populations.

Screened patients are defined as all patients who have originally met inclusion criteria and have signed the informed consent.

Randomized patients consist of all screened patients with a treatment arm allocated and recorded in the interactive response technology (IRT) database, regardless of whether the treatment was used or not.

For patient study status, the total number of patients in each of the following categories will be presented for the main 6-month period and 12-month study period separately, using a flow-chart diagram or summary tables:

- Screened patients: all patients who have originally met inclusion criteria and have signed the informed consent.
- Screen failure patients and reasons for screen failure.
- Randomized patients: all screened patients with a treatment arm allocated and recorded in the IRT database, regardless of whether the treatment was used or not.

- Safety population (as defined in Section 2.3.2, presented as treated).
- Treated but not randomized patients.
- Randomized but not treated patients.
- The ITT population (as defined in Section 2.3.1.1), analyzed as randomized.
- The per protocol population (Section 2.3.1.2), analyzed as randomized.
- The randomization strata (geographical region [Europe, US, Japan], type of diabetes [T1DM, T2DM], screening HbA1c categories [<8%, ≥8%], prior use of NovoLog/NovoRapid [Yes, No]) assigned by IRT will be summarized. The discrepancy between the strata assigned by IRT and the information reported on e-CRF will be listed for all randomized patients.
- Disposition for the main 6-month period:
 - Patients who completed the main 6-month treatment period (patients who have performed Visit 9 [Week 26] and who did not permanently discontinue treatment before Visit 9 [Week 26]),
 - Patients who permanently discontinued the IMP during the main 6-month treatment period, and the reasons for permanent treatment discontinuation,
 - Patient's decision for treatment discontinuation during the main 6-month period,
 - Patients who completed the main 6-month study period (patients who have performed Visit 9 [Week 26]),
 - Patients who prematurely discontinued the study during the main 6-month period, and the reasons for premature study discontinuation,
 - Status at last study contact of patients who prematurely discontinued the study during the main 6-month period.
- Disposition for the 12-month period:
 - Patients who completed the 12-month treatment period including 6-month extension (patients who have performed Visit 12 [Week 52] and who did not permanently discontinue treatment before Visit 12 [Week 52]),
 - Patients who permanently discontinued the IMP during the 12-month treatment period, and the reasons for permanent treatment discontinuation,
 - Patient's decision for treatment discontinuation during the 12-month period,
 - Patients who completed the 12-month study period (patients who have performed Visit 12 [Week 52]),
 - Patients who prematurely discontinued the study during the 12-month period, and the reasons for premature study discontinuation,
 - Status at last study contact.

For all categories of patients (except for the screened and nonrandomized categories) percentages will be calculated using the number of randomized patients as the denominator divided for different treatment group.

Patients with the following deviations will be identified and described in separate listings:

- Treated but not randomized.
- Randomized but not treated.
- Randomized but not treated as randomized.

Kaplan-Meier (KM) plots/estimates of the cumulative incidence of IMP discontinuation due to any reason, or due to AE, will be provided for the main 6-month and for the 12-month on-treatment period separately. Time to treatment discontinuation will be defined as the number of days from the first dose of IMP until the day of treatment discontinuation. All completers will be considered as censored observations. The censoring time will be the number of days from the first dose of IMP until the last dosing date.

A list of patients prematurely discontinued from the treatment, along with reasons for discontinuation, will be provided.

Patients treated without being randomized will not be considered as randomized and will not be included in any population. Their safety data will be listed separately

For any patient randomized more than once, only the data associated with the first randomization will be used in any analysis population. The safety experience associated with any later randomization will be assessed separately.

All critical or major protocol deviations (including randomization and drug-dispensing irregularities, see Section 2.2.1) will be summarized by treatment group among randomized patients (number and percentages).

Additionally, the analysis populations for safety and efficacy will be summarized in a table by patient counts on the randomized population:

- Efficacy population: ITT population, Per-Protocol population,
- Safety population,
- Anti-insulin antibody population.

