10.3.2 Permanent treatment discontinuation with investigational medicinal product(s)

Permanent treatment discontinuation is any treatment discontinuation associated with the definitive decision from the Investigator or the patient not to re-expose the patient to the IMP at any time.

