10.3.3 List of criteria for permanent treatment discontinuation

The patients may withdraw from treatment with the IMP if they decide to do so, at any time and irrespective of the reason, or this may be the Investigator's decision. All efforts should be made to document the reasons for treatment discontinuation and this should be documented in the e-CRF.

The following reasons lead to permanent discontinuation:

- At the patient's own request, ie, withdrawal of consent for treatment.
- If, in the Investigator's opinion, continuation with the administration of the study treatment would be detrimental to the patient's well-being.
- Inter-current condition that requires permanent discontinuation of the study treatment (eg, laboratory abnormalities according to the decision tree in Section 17, Appendix B) as long as the abnormality persists and if the casual relationship of the concerned event and the IMP is possible according to the Investigator's best medical judgment).
- Pregnancy.
- Specific request of the sponsor.

Any abnormal laboratory value or ECG will be immediately rechecked for confirmation before making a decision of permanent discontinuation of the IMP for the concerned patient.

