2.4.4.1.2 Sensitivity analysis

Sensitivity analyses will be conducted to assess the robustness of primary efficacy analysis with regard to missing data (5).

Description of missing data

The following analyses will be performed on the ITT population to explore the missing data frequency and pattern:

- As described in Section 2.2, KM plots/estimates of the cumulative incidence of IMP discontinuation will be provided by treatment group for the main 6-month period, with hazard ratio and 95% CI estimated using Cox regression model.
- Availability of HbA1c at each visit will be provided by treatment group according to the status of the patient (discontinued treatment or not).
- The number and disposition of patients with missing data will be described according to the availability for the primary efficacy analysis (Consolidated Standards of Reporting Trials [CONSORT] diagram according to missing data pattern).

- In order to explore missing data patterns for HbA1c, number and percentage of patients in each of the following categories will be presented by treatment group and patient status at Week 26 (Patient without permanent treatment discontinuation, patient with permanent treatment discontinuation):
 - Pattern 1: patients without baseline if any,
 - Pattern 2: patients with baseline but without post-baseline value during the main 6-month randomized period,
 - Pattern 3: patients with baseline and at least one post-baseline value during the main 6-month randomized period but not at Week 26,
 - Pattern 4: patients with baseline and Week 26 value during the main 6-month randomized period.
- Baseline characteristics and HbA1c values by visit will be presented by missing data pattern for each treatment group, using descriptive statistics and/or graphs.

Return to baseline analysis

To assess the robustness of primary efficacy analysis with regard to the imputation of missing data, a sensitivity analysis will be performed using a multiple imputation method that models a "return-to-baseline" for patients having missing data at Week 26.

For each patient in the SAR341402 and NovoLog/NovoRapid group in the ITT population, the missing HbA1c values at Week 26 will be imputed as equal to the patient's baseline plus an error. The error will be normally distributed with mean zero and standard deviation set equal to the estimated pooled standard deviation. No negative value will be allowed (in this case, another value will be redrawn).

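### SAP 2.2 plans Kaplan-Meier for stopping IMP due to AE; stops for other reasons are competing events, so that curve slightly overstates the incidence

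*SAP*

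**What the plan says.** SAP 2.2 (Disposition of patients) plans Kaplan-Meier plots and estimates. These "estimates of the cumulative incidence of IMP discontinuation due to any reason, or due to AE, will be provided", and they "will be provided for the main 6-month and for the 12-month on-treatment period separately". One estimator therefore serves both the any-reason curve and the AE curve.

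The time scale and censoring are set in three sentences:

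- Event time is counted in days, starting at a patient's first IMP dose and ending on the day treatment stops.
- On who is censored, the text is brief: "All completers will be considered as censored observations".
- A censored patient's time ends on the date of the last dose.

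Nothing says how a patient who stops for a non-AE reason enters the AE curve, and the SAP names no competing-risk estimator anywhere.

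Protocol 10.3.3 lists reasons for permanent discontinuation that need not involve an AE. The first is "At the patient's own request, ie, withdrawal of consent for treatment"; pregnancy and a sponsor request are others. Protocol 10.3.2 makes a permanent stop final: it is a decision "not to re-expose the patient to the IMP at any time".

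**The concern.** The SAP names its target as the cumulative incidence of stopping IMP due to AE, which is the share of patients who actually stop for that reason by a given day. Kaplan-Meier estimates that share only if the patients removed by censoring could still have had the event later. A patient who has permanently stopped for another reason cannot. If such patients are censored, one minus Kaplan-Meier describes a setting in which nobody ever stops for another reason, and it lies above the real incidence.

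At stake is the accuracy of a by-arm tolerability display. The trial is open-label, so other-reason stops could differ between arms, and the overstatement would then differ as well. The report would also show an AE curve ending above the crude percentage for the same event, with no explanation.

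**Working it through.** **What the plan implies for the AE curve.** Counting other-reason stops as events would reproduce the any-reason curve, so they cannot be events. The only censoring time given is the last dosing date. Applied to these patients, it removes them from the risk set when they stop. This is an inference, because the SAP states the rule for completers only.

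**Direction.** At each AE stop the Aalen-Johansen estimate rises by S(t−) × d/n. Here S is the probability of still being on IMP (no stop of any kind), d is the number of AE stops and n is the number at risk. One minus Kaplan-Meier uses the same d/n but multiplies it by the Kaplan-Meier curve for AE stops alone, which is never below S. One minus Kaplan-Meier is therefore never below Aalen-Johansen. The two agree when there are no other-reason stops.

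**Inputs.** The documents state no discontinuation rates, so there is no planned figure to reproduce. The AE incidence (a) and other-reason incidence (o) at the end of the period are assumptions, with constant cause-specific hazards. The arm size of 290 is from SAP 1.3 and is used only to express the excess in patients.

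**Formulas.**

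- Total cumulative hazard: H = −ln(1 − a − o)
- AE cumulative hazard: H_AE = H × a / (a + o)
- One minus Kaplan-Meier: 1 − exp(−H_AE)
- Overstatement: the last line minus a

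**Overstatement within an arm.**

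| True AE / other | H | H_AE | 1 − KM | Excess (points) | Relative | Per 290 patients |
|---|---|---|---|---|---|---|
| 2% / 8% | −ln(0.90) = 0.1054 | 0.0211 | 2.09% | 0.09 | 4% | 0.2 |
| 3% / 12% | −ln(0.85) = 0.1625 | 0.0325 | 3.20% | 0.20 | 7% | 0.6 |
| 5% / 20% | −ln(0.75) = 0.2877 | 0.0575 | 5.59% | 0.59 | 12% | 1.7 |

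**Difference between arms.** Take a true AE incidence of 3% in both arms.

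- Other-reason stops 5%: H = −ln(0.92) = 0.0834; H_AE = 0.0834 × 3/8 = 0.0313; 1 − KM = 3.08%.
- Other-reason stops 15%: H = −ln(0.82) = 0.1985; H_AE = 0.1985 × 3/18 = 0.0331; 1 − KM = 3.25%.

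The spurious difference is about 0.2 points (0.17), or half a patient in 290.

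**Check by simulation.** Kaplan-Meier and Aalen-Johansen were computed explicitly on 2000 simulated arms of 290, with nobody censored before the end of the period.

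- AE 2%, other 10%: 1 − KM averaged 2.10%, Aalen-Johansen 1.99%. The formula gives 2.11% for one minus Kaplan-Meier.
- AE 5%, other 20%: 1 − KM averaged 5.62%, Aalen-Johansen 5.03%.

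In both cases Aalen-Johansen equalled the crude proportion.

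**The case against.** The strongest reply is that the report will already hold the right number. SAP 2.2 gives counts of permanent IMP discontinuation by reason for both periods, with percentages on all randomized patients per arm, and a listing of every patient who stopped early with the reason. SAP 2.4.5.2 adds the number and percentage with a treatment-emergent AE leading to permanent discontinuation, overall and by MedDRA level. None of these carries the Kaplan-Meier bias. With fixed follow-up the crude proportion is essentially the Aalen-Johansen value at the end of the period. No test or decision rule rests on the AE curve, and the disposition section of the protocol (11.2) does not ask for it. All of this stands, and it is why the point is minor. It does not make Kaplan-Meier the right estimator for the quantity named.

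A reader might also infer more than the documents support:

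- **That the SAP orders other-reason stops to be censored.** It does not; it names completers only. Censoring is the natural reading. Even a reader who rejects it is left with an unspecified rule.
- **That the open-label design will produce a misleading difference between arms.** Nothing in the documents shows that other-reason stops will differ by arm. A gap as wide as 5% versus 15% moves the comparison by only about 0.2 points.
- **That the overstatement could approach 20%.** A relative figure of 19% needs 5% AE and 30% other-reason stops, that is, 35% stopping in total. The documents give no basis for that.
- **That the missing-data description is affected.** SAP 2.4.4.1.2 refers back to SAP 2.2 and says that "estimates of the cumulative incidence of IMP discontinuation will be provided by treatment group for the main 6-month period", but names no reason for stopping. The natural reading is any-reason discontinuation, for which Kaplan-Meier is appropriate.

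**Conclusion.** The point holds as a minor correction to one descriptive output. For the AE curve in SAP 2.2, one minus Kaplan-Meier with other-reason stops censored overstates the cumulative incidence. The excess is about 0.1 to 0.6 percentage points across the assumed range.

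The direction rests on the inferred censoring and on permanent stops being final, which the protocol states. The size rests on assumed incidences and constant hazards, because the documents give no rates. The any-reason curve, the missing-data description, the crude percentages by reason and the primary HbA1c analysis are unaffected.

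**What to change.** In SAP 2.2, keep Kaplan-Meier for discontinuation for any reason. For discontinuation due to AE, specify the cumulative incidence function (Aalen-Johansen) by treatment group. Treat permanent discontinuation for any other reason as a competing event and censor completers at their last dosing date. Apply this to both the 6-month and the 12-month on-treatment periods.

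The cost is one sentence in the SAP and one option in the SAS survival procedure (EVENTCODE). Reasons for permanent discontinuation are already recorded in the e-CRF (Protocol 10.3.3 and 10.3.4), so no new data are needed.
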